12. INFORMED CONSENT

A waiver of documented consent will be requested and once oral consent by the subject is obtained this consent will be used for the sole purpose of discussing the study with the subjects over the phone and performing the screening process as needed. The reason for this is because the only record linking the subject and the research would be the consent document and the principal risk would be potential harm resulting from a breach of confidentiality. In an effort to further protect the subject and their right to privacy, subjects will be screened for qualification prior to being asked to sign a written consent form to participate in the research project. Each subject will be asked whether the subject wants documentation linking the subject with the research, and the subject's wishes will govern. Additionally, the screening process presents no more than minimal risk of harm to subjects and involves no procedures for which written consent is normally required.

Once oral consent has been obtained, a research coordinator will screen the subjects over the telephone. Individuals interested in participating in this study will be given detailed explanation of the procedures, potential benefits, risks and discomforts of the study by the study researchers. A copy of the consent form will be mailed a minimum of 48 hours in advance to the individuals interested in participating in the study. The PI will obtain informed, written consent on the day of the study after ensuring the patients fully understand the procedures and risks/benefits. Subjects unable to give their own consent will not be included in the study. Subjects who have given a written consent will be given a copy of the signed consent form. The original consent will be kept in the subjects research file in a locked cabinet.

They will also be informed that participation in the registry is completely voluntary and will not directly impact the care that they receive at UCSD. Informed consent will be obtained in English for all English speakers. For patients who are not English speakers, consent will only be obtained in Spanish by a Spanish speaking provider or certified interpreter (in person or over the telephone). Documents will be used that are in the subject's primary language. Patients will be told that continued, qualified interpretative services to the participant will be provided.

Original consent forms will be kept on file by the study coordinator in the master research file. A copy of each will also be scanned into the patient's electronic medical record in the “media” tab where other consent forms can be found.

Spanish translated documents will be submitted to the IRB after approval of the English documents.

13. ALTERNATIVES TO STUDY PARTICIPATION

There are no alternatives to study participation. Subject may choose not to participate in this research study if they wish.

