The high mortality in untreated overlap syndrome patients is due to cardiovascular mortality, but the exact mechanisms are not yet known. However, some evidence suggests that pulmonary vasoconstriction and RV dysfunction may be an underlying mechanism. The prevalence of PH in overlap syndrome is much higher than in OSA alone. PH and RV dysfunction are associated with poor prognosis in COPD. The 5-year survival rate is only 36% in those whose initial mean pulmonary artery pressure (mPAP) is >25 mm Hg compared with 66% in those whose initial mPAP is <25 mm Hg. Moreover, severity of PH correlates negatively with survival (5-year survival ~15% with mPAP > 40 mm Hg vs ~55% with mPAP 20–40 mmHg). On the other hand, RV dysfunction and hypertrophy have also been described in otherwise uncomplicated OSA (figure 2). Although RV function can be abnormal in either disease, it may be worse in overlap syndrome due to the increased burden of hypoxemia and hypercapnia. However, the changes in RV function have not been well studied in patients with overlap syndrome. In addition, endothelial dysfunction of pulmonary vasculature plays an integral role in the pathogenesis of pulmonary hypertension (PH). The gold standard for early detection of endothelial dysfunction requires intracoronary or intra-brachial infusions of vasoactive agents. However, it is invasive with potential side effects of vascular or nerve injuries. Recently, several non-invasive techniques have been developed to assess endothelial function and one of them is peripheral arterial tonometry (PAT) in response to reactive hyperaemia. This technique evaluates the percentage change of flow from baseline to the maximum flow during reactive hyperaemia following a five minute ischemia of the distal forearm (achieved by blowing up a blood pressure cuff around the arm). The advantage of this technique is non-invasive, simple, and reproducible with less observer dependence comparing to ultrasound based technique. Therefore, we choose to use this technique to evaluate the endothelial function in this study. Furthermore, recognizing that COPD and OSA are both important contributors to secondary PH, clinicians would likely treat both underlying diseases. With COPD, long-term oxygen therapy can improve COPD mortality. In OSA, continuous PAP (CPAP) therapy can improve PH. However, there is no rigorous research on how patients with overlap syndrome should be treated.

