Treatment of hypoxemia in COPD alone has been shown to improve mortality. However, treatment of hypercapnia in COPD with nocturnal Bilevel has shown contradictory results. Of note, known OSA was excluded from the bulk of these above cited COPD studies. We postulate that COPD patients with concomitant OSA may be ideal candidates for positive pressure ventilation, since this intervention could treat both hypoxemia and hypercapnia.

Positive airway pressure therapy in overlap syndrome

Overlap syndrome patients are typically hypercapnic at more preserved levels of lung function than those with COPD alone (average forced expiratory volume in one second, FEV1 1.8 vs. 1.0 L). Therefore, overlap syndrome patients are likely to be particularly susceptible to pulmonary artery vasoconstriction due to intermittent hypoxemia and hypercapnia. OSA causes pharyngeal obstruction resulting in intermittent hypercapnia and hypoxemia. Accessory respiratory muscle atonia during REM sleep in patients with underlying COPD commonly leads to hypercapnia. By decreasing hypoxemia and hypercapnia, with resultant reduction of pulmonary artery vasoconstriction, treatment of overlap syndrome at night may well improve RV

(and LV) performance during the daytime. One uncontrolled study showed an improvement in gas exchange and FEV1 with CPAP therapy in overlap syndrome. Another prospective study showed a reduction in mortality and hospitalizations due to COPD exacerbations after CPAP therapy in overlap syndrome. Furthermore, we recently observed in 11,000 patients improved mortality in a dose response relationship with CPAP use in patients with overlap syndrome, although again lack of randomization limits definitive conclusions. To date, no prospective, randomized, controlled study has yet evaluated the effect of BiLevel therapy on clinical outcomes in overlap syndrome.

Rationale for using BiLevel vs. NOT

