BiLevel can treat both hypoxemia and hypercapnia. We will use BiLevel to treat OSA in COPD patients rather than conventional CPAP therapy because COPD patients are prone to hypoventilation during sleep (especially REM sleep) due to atonic accessory respiratory muscles. Nocturnal oxygen therapy (NOT) corrects nocturnal hypoxemia. NOT will be used in the control group because recurrent transient hypoxemia during sleep is frequent in patients with COPD, and nocturnal desaturation during sleep is an independent risk factor for increased cardiovascular complications. Previous studies of oxygen therapy in COPD have shown that NOT is safe, even in hypercapnic COPD patients. CPAP, however, has less predictable effects on hypoxemia or hypercapnia in overlap syndrome patients. Thus, by comparing BiLevel vs. NOT, we can independently assess the effect of sleep-related hypercapnia on RV hemodynamics. Also, it will allow us to test the hypothesis that treatment of both hypoxemia and hypercapnia will improve RV hemodynamic parameters compared with treatment of hypoxemia alone in patients with overlap syndrome.

Limitations of prior literature

Though it is known that untreated overlap syndrome has increased cardiovascular mortality compared to COPD, the mechanisms of cardiovascular dysfunction in overlap syndrome have not been studied. Moreover, prospective, randomized, controlled trials of BPAP therapy in overlap syndrome are lacking. Our study will provide insight into mechanisms of excess cardiovascular mortality in overlap syndrome. The interventional part of our study is a pilot study to help determine optimal treatment of overlap syndrome patients. The preliminary data, if encouraging, will be used to plan a larger multi-center clinical trial with longer duration of BiLevel therapy (with mortality, hospitalizations and COPD exacerbations as outcomes).

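### Section 13 says that nobody has an alternative to joining, which is wrong for the 40 Part Two patients, since the protocol itself describes PAP and oxygen used outside the trial

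*Protocol*

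**What the plan says.** Section 13 of the protocol has two sentences. The first is "There are no alternatives to study participation". The second is "Subject may choose not to participate in this research study if they wish". Neither distinguishes Part One from Part Two, and neither names a treatment.

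Part Two (Sections 9 and 10) takes 40 overlap syndrome patients from Part One and randomises them 1:1, 20 per arm, to BiLevel plus oxygen if needed or to nocturnal oxygen alone. The final visit is at 6 months. All have an AHI above 15/hour and none is on oxygen or PAP at entry.

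Section 7 describes how such patients are treated in practice:

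- Where COPD and OSA both contribute to pulmonary hypertension, "clinicians would likely treat both underlying diseases". Long-term oxygen is credited with improving COPD mortality, and "In OSA, continuous PAP (CPAP) therapy can improve PH".
- On CPAP in overlap syndrome itself: "Another prospective study showed a reduction in mortality and hospitalizations due to COPD exacerbations after CPAP therapy in overlap syndrome". The investigators add that "we recently observed in 11,000 patients improved mortality in a dose response relationship with CPAP use in patients with overlap syndrome", and note that the data are not randomised.
- On the choice of device: "We will use BiLevel to treat OSA in COPD patients rather than conventional CPAP therapy".

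Section 7 also says that "there is no rigorous research on how patients with overlap syndrome should be treated", and that CPAP acts less predictably on hypoxemia and hypercapnia in these patients.

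**The concern.** Section 13 is where the protocol records what a person could do instead of joining. A flat denial of alternatives suits a study that only measures. Part Two assigns treatment, and a patient considering it has a 1-in-2 chance of oxygen alone for 6 months. Whether PAP can be had from one's own physician without joining bears directly on that decision. If the protocol's statement carried through to the consent discussion, patients would be deciding on a false premise about their options.

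This is a positive statement in the current text that other sections contradict. It is not a detail that a protocol would leave to a statistical analysis plan.

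**Working it through.** No formula decides this. The check sets Section 13 beside the rest of the protocol and asks, for each part, whether an alternative exists.

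**Part One.** It is cross-sectional and assigns no therapy. There is nothing to have instead of participation except not participating. Section 13 is acceptable here.

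**Part Two.**

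1. *Is there a treatment outside the trial that the trial does not offer?* Yes, CPAP. Section 7 names it as a therapy for OSA, reports a prospective study and the investigators' own data on its use in overlap syndrome, and explains that BiLevel was chosen in its place. It is in neither arm.
2. *Are the trial's own treatments obtainable outside it?* Yes. Section 9 excludes patients already using oxygen, BiLevel or CPAP. That exclusion only makes sense if people in this population already receive them.
3. *Do these patients have a route to such care?* Section 9 recruits through outpatient pulmonary and sleep medicine clinics and refers to a treating pulmonologist.
4. *Does any other text supply the missing alternative?* The second sentence of Section 13, the opt-out in Section 11 and the voluntariness text in Section 12 all say that a person may decline. None says what treatment a person who declines can have.

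The answers to 1 and 2 contradict Section 13 for Part Two, and 3 and 4 do not restore it. The strongest support is the text on CPAP in overlap syndrome together with the exclusion of current users.

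Two supporting passages carry less weight. The remark that clinicians would treat both diseases is made about contributors to pulmonary hypertension, which is not an entry criterion. The word 'conventional' contrasts CPAP with BiLevel and does not call CPAP the standard of care for overlap syndrome.

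**How many people the sentence misdescribes.**

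- Part Two: 2 arms × 20 = 40 patients, as Sections 9 and 10 both state.
- Against the Section 10 total: 40 / 150 = 26.7%, about 27%.
- Against the Section 9 group sizes: 40 / (150 + 50 + 50) = 40 / 250 = 16%.
- Assigned oxygen alone: 20 / 40 = 50%.

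The two denominators arise because Section 9 targets 150 overlap patients and Section 10 targets 50. The count of 40 is the same under both. These are counts of people, not effect sizes.

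**The case against.** **The best treatment is unknown.** The protocol says that rigorous research in overlap syndrome is lacking, that the CPAP data are not randomised and that CPAP is less predictable. All of this is true and it supports randomising. It concerns which treatment is best, not whether one can be obtained, so it does not make Section 13 correct.

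**Patients are informed by the consent form, not by Section 13.** This stands as a limit on the consequence. The form was not available. Section 12 says that it is mailed at least 48 hours ahead and that procedures, benefits, risks and discomforts are explained in detail. A reader might infer that patients were in fact misinformed. The protocol alone does not show that; it shows one wrong statement in the protocol.

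**Much of the care is the same inside and outside the trial.** This stands in part. Section 9 continues COPD medication in both arms, so COPD drug treatment is not an alternative to joining. BiLevel and oxygen are also given in the trial, but by random assignment, so a patient who wants one of them in particular still has a reason to know that it can be prescribed clinically.

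**Section 14 might seem open to the same criticism**, since its Phase Two text does not spell out that oxygen alone leaves airway obstruction untreated. That is an omission, and no sentence there is shown to be false. Section 7 openly describes the comparator as treating hypoxemia alone. The point is not pressed.

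**Conclusion.** Section 13 is wrong as written for the 40 Part Two patients and acceptable for Part One. Confidence in the contradiction is high, because both sides of it stand in the same document. Confidence about what patients are told is limited by the unseen consent form.

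The weight is minor to moderate. It is a matter of consent wording and patient protection and touches no estimate, power calculation or analysis.

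Two stronger readings should be resisted:

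- **That the oxygen arm is left unmonitored or kept from PAP.** Section 9 plans visits at 2 weeks, 3 months and 6 months with telephone contact, and nothing in the protocol bars a patient from withdrawing or starting PAP elsewhere.
- **That the mortality figures in Section 7 measure the harm.** Section 7 gives 42.2% in untreated overlap syndrome against 24.2% in COPD only. These are observational, cover a median of over 9 years and compare different patient groups. They say nothing quantitative about 6 months of oxygen alone, and no excess harm is estimated here.

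The conclusion assumes only that treatments which the protocol describes as in use, and screens for at entry, can be obtained by patients under specialist care.

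**What to change.** Limit the existing sentence in Section 13 to Part One. Add one sentence for Part Two, for example: *For Part Two, PAP (CPAP or BiLevel) or oxygen prescribed by the patient's own physician is available without joining the study.* Then check that the consent form says the same and amend it if it does not.

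The cost is a wording change in one section, and in the consent form if needed. Arms, endpoints, visits and sample size are unchanged. The downside is that a few eligible patients may decline Part Two once the alternative is stated.

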14. POTENTIAL RISKS

As we anticipate minimal risk from our studies, we doubt any subject will need to be removed or excluded from the study.

There is a very small risk of loss of subject confidentiality. We will protect all subject information to the best

of our ability so this will not happen.

Phase One Study

We believe the risks and discomforts to be small. All patients will be screened for standard contraindications (e.g. implanted device and foreign bodies) for cardiac MRI. If contraindicated, patients will not be enrolled to the study. All participants will be given a full description of the risks associated with MRI scanning as part of informed consent process. Gadolinium contrast, which is required for cardiac MRI, has been associated rarely with the syndrome of nephrogenic systemic fibrosis in patients with moderate to severe kidney diseases. Therefore, moderate or severe kidney disease is one of the exclusion criteria to minimize the potential risk. Small number of patients may experience anxiety or claustrophobia due to the confined space of MRI scan. However, the anxiety or claustrophobia often, if not always, resolves after termination of the scan. We and other investigators have accomplished similar studies without incident.

Phase Two Study

We believe the risks and discomforts to be small. All patients will be screened for standard contraindications (e.g. implanted device and foreign bodies) for cardiac MRI. If contraindicated, patients will not be enrolled to the study. All participants will be given a full description of the risks associated with MRI scanning as part of informed consent process. Gadolinium contrast, which is required for cardiac MRI, has been associated rarely with the syndrome of nephrogenic systemic fibrosis in patients with moderate to severe kidney diseases. Therefore, moderate or severe kidney disease is one of the exclusion criteria to minimize the potential risk. Small number of patients may experience anxiety or claustrophobia due to the confined space of MRI scan. However, the anxiety or claustrophobia often, if not always, resolves after termination of the scan. We and other investigators have accomplished similar studies without incident. Nocturnal oxygen therapy (NOT) and BPAP therapy have both been used in COPD patients in numerous previous research studies without significant reportable risks. NOT and BiLevel therapy will be closely followed and titrated to minimize any discomfort or adverse effects.

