9. RESEARCH DESIGN AND METHODS

Part One Study Objective: The first part is a cross-sectional cohort study comparing subjects with overlap syndrome to those with COPD alone and those with OSA alone.

Subjects: Our target sample will be 150 subjects in the overlap syndrome group. This group will include subjects with age > 18 years with known or suspected diagnosis of overlap syndrome, which we will define as COPD: Global Obstructive Lung Disease (GOLD) stage 2 disease or higher and OSA: apnea-hypopnea index (AHI) >15/hour. We will exclude patients already using oxygen or BiLevel/CPAP, patients with known or suspected renal failure (creatinine >1.5 mg/dl), pregnant women (due to possible risk to the fetus due to cardiac MRI and gadolinium contrast), patients with atrial fibrillation or frequent (>10/h) premature ventricular contractions (since these may complicate cardiac MRI sequences) and patients with known contraindications to

MRI: metallic (ferromagnetic) implants, cardiac pacemakers, past history of claustrophobia.

The control subjects will be divided into two groups, one with COPD only (50 subjects) and the other with OSA only (50 subjects). The COPD control group will include subjects with known COPD diagnosed by a pulmonologist (GOLD stage 2 or higher). The OSA control group will include subjects with a known diagnosis of OSA diagnosed by a sleep specialist (apnea-hypopnea index, AHI >15/hour). The exclusion criteria for the control subjects will be the same as the overlap syndrome subjects.

Study enrollment: All patients will be recruited through the outpatient pulmonary and sleep medicine clinics at the UCSD hospitals. Poster advertisements will be placed in the outpatient clinics to encourage subject recruitment through physician referral. COPD patients in outpatient pulmonology clinics who express interest in enrolling in the study will be approached by one of the study investigators to obtain informed consent. COPD patients meeting eligibility criteria will be screened for OSA risk and scheduled for overnight polysomnography (PSG) as part of baseline visit. COPD patients with coexisting OSA will be enrolled in the overlap syndrome group. COPD patients without coexisting OSA will be enrolled in the COPD only control group. If COPD patients are referred for clinically indicated sleep studies, these patients will also be eligible for participation (as either COPD only or overlap syndrome patients), depending on the results of the sleep study.

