
Part Two Study Objective: The second part of the study is a prospective, parallel-group, randomized, controlled pilot study examining the effect of BiLevel therapy (and NOT if needed) vs. NOT alone in patients with overlap syndrome (20 subjects in each treatment arm).

Study Intervention: This will be done in 40 subjects in overlap syndrome group only who provide informed consent (20 subjects in each treatment arm). Randomization of overlap syndrome subjects to nocturnal BiLevel therapy (plus oxygen if needed based on saturations <88% while on stable bi-level settings), and NOT only will be done using sequentially-numbered, opaque, sealed envelopes using 1:1 allocation ratio. Regular therapy with COPD medications including long-acting anticholinergic medications and inhaled corticosteroids will be continued as advised by the treating pulmonologist. Only COPD subjects with stable clinical course during the duration of study intervention will be called for follow-up visits as any COPD exacerbations during the course of study intervention may potentially confound the follow-up study results. The time commitment for this initial visit will require up to 2-3 hours of the subjects time.

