Follow-up visits: The first follow-up visit will be done 2 weeks after starting treatment to ensure compliance and determine any discomforts due to treatment. At this visit phlebotomy will be done to take blood samples for venous gas analysis. Subjects will be asked to complete all questionnaires as outlined in the baseline visit. Second follow-up visit will be done 3 months after starting treatment to ensure compliance with treatment and determine any study related discomforts. Subjects will be asked to complete all questionnaires and cognitive function testing as outlined in the baseline visit. The final follow-up visit will be done 6 months after starting study treatment. Throughout the course of the study, regular telephone contact will be maintained by the study staff to ensure adherence to therapy and to address issues as they arise. At this final follow-up visit, all the tests done at baseline visit (except PSG) will be repeated as well as all afore mentioned questionnaires and cognitive function testing. This pilot study will generate preliminary data for a multi-center clinical trial with longer duration of PAP therapy and mortality, hospitalizations or COPD exacerbations as outcomes, if we find encouraging results. If the subject is called for follow-up visits, first follow up visit will require a time commitment of 15-20 minutes (2 week mark of starting treatment) for and the other two follow up visit will require a time commitment of 25-30 minutes (one at the 3-month mark of starting treatment and one final follow up visit). During the course of the 2 week, 3 month and 6 month periods between follow up visits, study staff may contact the patient to ensure adherence to therapy and address issues as they arise. While these phone call encounters may vary in time based on the subject's needs, typically they should require no more than 5-10 minutes of the subject's time.

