10. HUMAN SUBJECTS

We anticipate recruiting a total of 150 patients for phase one study: 50 patients with overlap syndrome, 50 patients with COPD, and 50 patients with OSA, age and gender matched to the overlap syndrome patients. For the phase two study, we aim to recruit 40 patients among the overlap syndrome patients who participated in phase one.

Phase One Study:

This group will include subjects with age > 18 years with known or suspected diagnosis of overlap syndrome, which we will define as COPD: Global Obstructive Lung Disease (GOLD) stage 2 disease or higher and OSA: apnea-hypopnea index (AHI) >15/hour. We will exclude patients already using oxygen or BiLevel/CPAP, patients with known or suspected renal failure (creatinine >1.5 mg/dl), pregnant women (due to possible risk to the fetus due to cardiac MRI and gadolinium contrast), patients with atrial fibrillation or frequent (>10/h) premature ventricular contractions (since these may complicate cardiac MRI sequences) and patients with known contraindications to MRI: metallic (ferromagnetic) implants, cardiac pacemakers, past history of claustrophobia. The control subjects will be divided into two groups, one with COPD only (50 subjects) and the other with OSA only (50 subjects). The COPD control group will include subjects with known COPD diagnosed by a pulmonologist (GOLD stage 2 or higher). The OSA control group will include subjects with a known diagnosis of OSA diagnosed by a sleep specialist (apnea-hypopnea index, AHI >15/hour). The exclusion criteria for the control subjects will be the same as the overlap syndrome subjects.

Phase Two Study:

40 patients in overlap syndrome group recruited during phase one study will be invited to participate in phase two study. The overlap syndrome patients who provide informed consent will be randomized into the two treatment arms (20 subjects in each treatment arm).

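### Section 14 relies on an exclusion of moderate or severe kidney disease, but the eligibility cut (creatinine >1.5 mg/dl) can admit moderate disease, and no renal result has to be read before contrast

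*Protocol*

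**What the plan says.** Section 14 gives the reason for a renal exclusion: "Gadolinium contrast, which is required for cardiac MRI, has been associated rarely" with nephrogenic systemic fibrosis in moderate to severe kidney disease. It then states the safeguard: "Therefore, moderate or severe kidney disease is one of the exclusion criteria to minimize the potential risk". The same text stands under Phase One and Phase Two.

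The eligibility text is in Sections 9 and 10. Both exclude "patients with known or suspected renal failure (creatinine >1.5 mg/dl"), and Section 9 extends this to the comparison groups: "The exclusion criteria for the control subjects will be the same as the overlap syndrome subjects". There is no eGFR limit, no adjustment for age or sex, and no separate criterion for moderate disease.

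On timing, the baseline visit in Section 9 includes a renal profile and a cardiac MRI. For the final visit at 6 months, Section 9 says "all the tests done at baseline visit (except PSG) will be repeated", so both the renal profile and the contrast MRI are done again. The study endpoints list the renal profile as a secondary endpoint.

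**The concern.** The risk section describes a protection that the eligibility section does not clearly contain. A coordinator who follows Sections 9 and 10 to the letter enrols anyone without known or suspected renal failure whose creatinine is 1.5 mg/dl or lower. A single creatinine value corresponds to quite different kidney function by age and sex, so some of those subjects may have the moderate disease that Section 14 says is excluded. They would then receive gadolinium at baseline and, if randomised, again at 6 months. The blood test that would reveal this is already drawn, but nothing makes the scan depend on its result.

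**Working it through.** **Step 1: the texts side by side.** Section 14 excludes moderate or severe kidney disease. Sections 9 and 10 exclude renal failure, with creatinine >1.5 mg/dl in brackets. Nothing equates the two terms, and moderate is not defined. The mismatch in wording needs no outside input.

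**Step 2: what the cut admits.** Inputs from the protocol: creatinine limit 1.5 mg/dl (Sections 9 and 10); men and women aged 18 to 79 (Section 11). Inputs assumed: the eGFR equations, without race terms, and the boundary for moderate. With S = creatinine in mg/dl, and S above the reference value k (0.7 for women, 0.9 for men):

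- CKD-EPI 2009: 141 × (S/k)^−1.209 × 0.993^age (× 1.018 if female)
- MDRD: 175 × S^−1.154 × age^−0.203 (× 0.742 if female)
- CKD-EPI 2021: 142 × (S/k)^−1.2 × 0.9938^age (× 1.012 if female). This postdates the protocol version and serves only as a check.

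Worked case, a woman of 70 at creatinine 1.5 (eligible):

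- CKD-EPI 2009: 141 × 1.018 × 0.398 × 0.612 = 34.9
- MDRD: 175 × 0.742 × 0.626 × 0.422 = 34.3
- CKD-EPI 2021: 37.3

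eGFR in mL/min/1.73 m2 for other eligible subjects:

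| Subject | Creatinine | CKD-EPI 2009 | MDRD | CKD-EPI 2021 |
|---|---|---|---|---|
| Woman, 60 | 1.5 | 37.5 | 35.4 | 39.6 |
| Woman, 70 | 1.4 | 38.0 | 37.2 | 40.5 |
| Woman, 70 | 1.3 | 41.5 | 40.5 | 44.2 |
| Woman, 79 | 1.5 | 32.8 | 33.5 | 35.2 |
| Man, 60 | 1.5 | 49.9 | 47.7 | 53.0 |
| Man, 70 | 1.5 | 46.5 | 46.3 | 49.8 |
| Man, 79 | 1.5 | 43.7 | 45.1 | 47.1 |

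**Step 3: sensitivity to the boundary.** Results are in the order CKD-EPI 2009 / MDRD / CKD-EPI 2021.

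- Below 60: eligible women of 70 fall under it from creatinine 0.96 / 0.92 / 1.01 up to 1.5, and men of 70 from 1.21 / 1.20 / 1.28 up to 1.5.
- Below 45: women of 70 from 1.22 / 1.19 / 1.28 up to 1.5. Men only from age 75, and only on CKD-EPI 2009.
- Below 30: nobody up to age 79. The lowest value is 32.8.

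**Step 4: what stands between a subject and the contrast dose.** At baseline, eligibility is implied to be settled before the MRI, but no rule says that the baseline renal profile must be read first. For Phase Two, Section 10 adds only consent: "The overlap syndrome patients who provide informed consent will be randomized into the two treatment arms (20 subjects in each treatment arm"). The MRI screening in Section 14 is an enrolment step with non-renal examples: "All patients will be screened for standard contraindications (e.g. implanted device and foreign bodies) for cardiac MRI". The one condition for being called back is "Only COPD subjects with stable clinical course during the duration of study intervention will be called for follow-up visits", which Section 9 explains by COPD exacerbations. At 6 months the renal profile and the MRI belong to the same visit, with no order, no review and no stopping value. Up to 40 randomised subjects are due this second scan; that is a ceiling, because only stable subjects are called back.

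**The case against.** The best reply is that Section 14 sets no second criterion. It points back to the exclusion list, which contains one renal item, so creatinine >1.5 mg/dl may simply be the working definition of moderate or severe, and the phrase known or suspected leaves the investigator room to exclude more. That reading is possible. However, the protocol does not state it, the qualifier attaches to renal failure, and on the equations above the cut would be a poor definition of moderate for older women.

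A second reply is that the equations and boundaries come from outside the protocol and that the answer changes with the boundary. This is true, which is why the range is shown. At 60 the gap affects both sexes, at 45 almost only women, and at 30 no one. The documents cannot choose between these and do not say at what eGFR the risk becomes material.

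Three stronger readings are tempting and should not be drawn. A reader might infer that kidney function is not rechecked at 6 months; Section 9 repeats the baseline tests, renal profile included, and what is missing is review before contrast. A reader might infer that severe disease is let in; the figures show that it is not. A reader might also cite the plan in Section 11 for equal numbers of men and women to argue that many women face the second scan; that sentence concerns OSA subjects and controls, whereas only overlap subjects are rescanned, and no sex ratio is given for them.

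**Conclusion.** The point holds in limited form. Sections 9 and 10 as written do not fully deliver the exclusion that Section 14 offers as its protection. On the assumed equations, the cut removes eGFR below 30 but can leave subjects between about 33 and 59, most clearly older women. At neither visit does the already planned renal profile act as a check before gadolinium. How many subjects this would touch cannot be derived from the protocol, and by its own account the harm is rare. Sample size, endpoints and comparisons are unaffected. It is a low-severity correction of safety and eligibility text. The mismatch in wording and the missing review rest on the protocol alone; the size of the gap rests on the assumed equations and on how moderate is defined.

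**What to change.** Put one renal criterion in Sections 9, 10 and 14, preferably an eGFR limit with the equation named and the threshold chosen by the clinical team. If creatinine >1.5 mg/dl is kept, reword Section 14 to say that severe disease is excluded but moderate disease is not fully excluded. In either case, require the renal profile to be drawn and read against the criterion before each gadolinium dose, including the 6-month scan, and state that a value beyond the limit stops the contrast scan.

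The cost is wording in three sections and one check per scan, on blood that is already collected. A few subjects may become ineligible, more with a limit of 60 than with 45. Keeping the creatinine cut and correcting Section 14 leaves the entry criterion unchanged. A subject who crosses the limit by 6 months would lose the contrast scan, so the protocol should say how such a subject's final MRI is handled.
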